#### 4. Subject Recruitment and Screening

This research study will be conducted at the Penn Center for Women's Behavioral Wellness (PCWBW), which is a clinical research endeavor in the Departments of Psychiatry and Obstetrics and Gynecology. Women will be recruited for this study by paid advertising, home mailings, and flyers and brochures in doctor's offices, libraries, and local stores. We will also be utilizing the Penn Data Store analysis in which we will request names, phone numbers, home addresses and email addresses for menopausal women between the ages of 48-60. Women who provide email addresses acquired via the Penn Data Store may be contacted via email, including an e-letter and a link to a survey assessing their qualification for study participation. Women who do not provide an email address may be contacted via a letter mailed to the provided address and/or by a phone call to the number provided to us. All women who contact PCWBW regarding study participation will have the study explained to them using the IRB approved phone script. Following the phone script all women who express interest in the study will have the option to complete a phone interview to determine eligibility. We have requested a waiver of documentation of informed consent to complete this interview. Women will also have the option to complete the ACE interview at the time of their phone interview. Women who appear to meet the entrance criteria after a brief phone screen will be scheduled for an in-office appointment in the Program's private office setting at [name]. During recruitment, potential participants will be explained that to offset their time commitment, they will be compensated \$200 for each test day. In addition, they will receive an additional \$250 if all four tests are completed, which encourages participants to complete the study. Recruitment materials have been previously submitted to and approved by the IRB.

#### 5. Early Withdrawal of Subjects

Early withdrawal of subjects may occur for the following reasons:

- 1. If the subject fails to return for visits.
- 2. Failure to locate the subject.
- 3. The subject withdraws their consent for participation.
- 4. The PI determines that the subject is no longer eligible for participation in the study.

A subject can withdraw their consent for participation in this study by contacting the study PI and or the research staff personnel who is following them in the study via telephone and informing them of their decision. In this case it would be preferable if the subject is willing to come in to the office for a debriefing regarding whether or not to continue estrogen treatment under the care of their personnel physician. If this is not possible, then the PI will speak with the subject by telephone to conduct this debriefing and find out whether or not the subject plans to stay on estrogen treatment. The subject's decision to withdraw and their disposition upon withdrawing from the study will be recorded in their research chart.

#### 6. Vulnerable Populations:

Children, pregnant women, fetuses, neonates, or prisoners are not included in this research study.

#### 7. Populations vulnerable to undue influence or coercion

Penn students and employees (both of appropriate age and study criteria), and economically disadvantaged persons, are welcome to participate in this study. The participants will be appropriately consented and their information will be kept in a locked cabinet, filed by a code, in a locked room that only the research study personnel has access to.

#### STUDY DESIGN

	Subject met at CHPS/PCWBW and initial assessments conducted; this includes the blood draw conducted by research nurse to determine estrogen, progesterone, serum hormone binding globulin, DHEA, and
7:30 AM	tryptophan levels
8:00 AM	Subject begins ingestion of 70 capsules with nurse present
8:30 AM	Subject completes ingesting capsules
2:00 PM	Assessments and memory testing
	Blood draw conducted by research nurse to determine change in free and
2:30 PM	total tryptophan
3:00 PM	Begin fMRI scan
3:45 PM	Post-scan recognition test
4:00 PM	Subject given meal and discharged after seeing a physician

# METHODS

# 1. Study Instruments

We will collect the following information and administer the following instruments during the screening phase after obtaining written, informed consent from each participant. Those assessments in **bold font** will also be administered on test days. Those in *italics* will only be collected during admission and on test days 2 and 4. \*\*Please note the ACE questionnaire will typically be administered verbally over the phone prior to presenting for the first in-office visit, however, women who do not want to complete the assessment over the phone will be given the option to complete the assessment in-office. The ACE will be administered a second time at test day three to assess the reliability of participant report. All discrepancies between initial ACE report and follow-up ACE will be documented and clarified with the participant.

- 1. Demographic information including age, education, marital status, race, income and insurance status.
- 2. Full gynecologic history including age at menarche, menstrual cycle length/regularity and menstrual cycle-related changes in mood and behavior, obstetrical history, mood related to pregnancies, and onset of menopausal symptoms and menstrual irregularity.
- 3. Information about family history of psychiatric disorders, alcoholism, and nicotine dependence in parents and siblings (obtained from subject report).
- 4. Structured Clinical Interview for Diagnosis (SCID) based upon the DSM-IV: The SCID interview is a widely used clinical interview to assess the presence of lifetime and present history of psychiatric and substance dependence disorders (First et al., 1997).
- 5. Mini-Mental State Examination (MMSE): MMSE is a brief quantitative screening measure of cognitive status. With a total 30 possible points, the instrument measures orientation, auditory registration, working memory, recall, language, and constructional skills.
- Clinician Administered PTSD Scale (CAPS): The CAPS is a 30-item structured interview that corresponds to the DSM-IV criteria for PTSD. The CAPS can be used to make a current (past month) or lifetime diagnosis of PTSD or to assesses symptoms over the past week. (Blake et al., 1995)
- 7. Traumatic Life Events Questionnaire (TLEQ): The TLEQ is a 23-item self-report measure of 22 types of potentially traumatic events including natural disasters, exposure to warfare, robbery involving a weapon, physical abuse and being stalked. The last question asks respondents to identify the one event that "causes you the most distress" among those endorsed. Respondents

are also asked about their age upon first occurrence, date of last occurrence, and amount of distress the event causes. This measure is commonly used for research purposes (Kubany et al, 2000).

- 8. \*\*Adverse Childhood Experiences (ACE): The ACE is used to determine a person's number of experienced adverse events prior to age 18. Exposure to one category (not incident) of ACE, qualifies as one point. When the points are added up, the ACE Score is achieved. An ACE Score of 0 (zero) would mean that the person reported no exposure to any of the categories of trauma listed as ACEs above. An ACE Score of 9 would mean that the person reported exposure to all of the categories of trauma listed above (Felitti et al., 1998).
- 9. Brief COPE: This short scale assesses how and how successful an individual's coping ability is when faced with adversity. (Carver, 1997).
- 10. Social Support Scale (SSS): The SSS assesses the amount of perceived social support individual's believe they have. (Zimet et al., 1998)
- 11. Utian Quality of Life Questionnaire (UQoL): The Utian QoL questionnaire is a brief instrument, which measures QoL during the perimenopausal years with 23 questions, demonstrating four separate intercorrelated domains (Utian et al., 2002).
- 12. **The Speilberger State-Trait Anxiety Scale (STAI)**: is a commonly used measure of trait (current) and state anxiety (general) (Spielberger et al.,1983). All items are rated on a 4-point scale (e.g., from "Almost Never" to "Almost Always"). Higher scores indicate greater anxiety.
- 13. Hamilton Depression Scale (HAM-D): The HAM-D is a clinician-rated instrument widely used to assess severity of depressive symptoms (Hamilton, 1960).
- 14. **The Profile of Mood States** (**POMS**): The POMS asks subjects to rate their mood over the last week (or other defined period of time), according to 65 adjectives, such as "friendly," "listless," and "on edge," using a 5-point Likert scale. The psychometric properties of this commonly-used test are well characterized (McNair et al., 1992).
- 15. Perceived Stress Scale (PSS): The PSS is the most widely used psychological instrument for measuring the perception of stress. It is a measure of the degree to which situations in one's life are appraised as stressful. Items were designed to tap how unpredictable, uncontrollable, and overloaded respondents find their lives. The 10-item scale also includes a number of direct queries about current levels of experienced stress. The PSS was designed for use in community samples with at least a junior high school education. The items are easy to understand, and the response alternatives are simple to grasp. Moreover, the questions are of a general nature and hence are relatively free of content specific to any subpopulation group. The questions in the PSS ask about feelings and thoughts during the last month. In each case, respondents are asked how often they felt a certain way (Cohen at al., 1983).
- 16. **Visual Analogue Scale (VAS)**: A VAS instrument listing 17 adjectives, including "talkative," "drowsy," and "nervous," and allowing subjects to mark how much of each they feel by choosing a point on a horizontal line will be used as another measure of mood.
- 13. Daily Hot Flash (HF) Diary: Women will be given a form to use in reporting the number of vasomotor events and their severity. Subjects will be instructed to complete this form daily throughout the course of their study participation. Women will rate each HF on a scale of 1 to 4 with 1=mild to 4=very severe. The score is calculated by multiplying the total number HFs by their severity score and summing the results for each day. The mean for the week prior to testing and the 6th week of ET or PT will be compared. This method for assessing HF severity has been validated in a series of pharmacologic trials. \*This rating is only given to participants who presently report experiencing hot flashes.
- 14. Beck Depression Inventory (BDI): The BDI was originally developed to detect, assess, and monitor changes in depressive symptoms among individuals. The sum of scores on the BDI

indicates the severity of depressive symptoms. In the general population, a score of  $\geq$  21 represents depression.

15. *Pittsburgh Sleep Quality Index (PSQI):* The PSQI questionnaire is used to assess recent quality of sleep and sleep disturbance (Buysse et al., 1989).

Additionally, all subjects will undergo a blood draw that includes a cholesterol screen and urine pregnancy test (if perimenopausal) during the screening process. The PI will also administer an ECG at this time to rule out for cardiovascular disease. Subjects must also provide documentation of having had a normal mammogram within the previous year, and a normal PAP and pelvic exam within the previous three years.

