#### OBJECTIVES

**Specific Aim 1:** To replicate and extend our previous behavioral findings of an interaction between ET and TRP-D on verbal memory in a group of early menopausal women randomized to receive ET (n=28). In a previous behavioral study of TRP-D and ET in healthy menopausal women (Amin et al., 2006b), we observed that TRP-D interfered with verbal memory to a lesser extent following ET than before. *In a new sample of women, we again hypothesize* (**H1.1**) *that paragraph recall performance and verbal paired-associates learning will decline as a result of TRP-D, but that ET will attenuate this decline.* In our previous study, we also found that length of hypogonadism (measured by months since last

menstrual period) was significantly associated with waning verbal memory performance. However, we did not have sufficient power with 18 women to detect whether the magnitude of ET effects differed based on length of time since menopause. *In this larger sample of 28 women, we hypothesize* (H1.2) *that women who have more recently experienced menopause will benefit more from ET than later menopausal women.* 

**Specific Aim 2:** To evaluate the extent to which effects of ET and TRP-D on verbal working memory are mediated through the dorsolateral prefrontal cortex. Previous neuroimaging studies have associated ET with improved working memory performance and increased dorsolateral prefrontal cortex (DLPFC) activation (Duff & Hampson 2000; Shaywitz et al., 1999). However, it is unclear whether TRP-D has an effect on working memory (Harrison et al., 2004; Riedel et al., 2003). It is hypothesized (**H2.1**) that ET will increase DLPFC activation during working memory more so than PT, but there will be no effect of TRP-D and no interaction between estrogen and serotonin effects in either the ET or PT groups. Very few fMRI studies have examined the impact of practice or rescanning on behavioral measures or the BOLD response during cognitive tasks. We seek to fill that void with the proposed study by including a placebo arm. Since submission of the A2 application, we have obtained test-retest data from our MR colleagues ([name], Ph.D.) demonstrating that with our new sample size of 28 women receiving ET and 14 women receiving placebo we can adequately test our hypothesis regarding ET and TRP-D effects on DLPC activation during the proposed working memory task.

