# 3. Method for Assigning Subjects to Groups

After completing the first two TRP depletion test sequences, participants will be randomized to receive either treatment with 17β-estradiol (Vivelle Dot® 0.10 - 0.15 mg/day) or a look-alike placebo patch for a total of 8 weeks. The research pharmacist who is responsible for dispensing the estrogen or placebo patches will also be responsible for the randomization of all subjects together with the statistician on the study. Randomization will be blocked and stratified. We will use a block size of 3 to be able to maintain a 2:1 ratio of estrogen to placebo within each stratum. To stratify randomization based upon time since last menstrual period by tertiles (1st=0-40 mos; 2nd=40-80 mos; 3rd=80-120 mos), we will prepare separate randomization tables for each stratum. The research pharmacist, PI, and research project manager will know to which group the subject has been randomized. The research pharmacist, PI or research project manager can be reached at any time should it become necessary to unblind a study participant immediately. The subject and all other study-related personnel (clinicians, raters, fMRI technicians, etc.) will be blind to subject assignment.

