# STUDY PROCEDURES

# 1. Detailed Description

This study involves TRP depletion, evaluation of cognition, and the use of fMRI during cognitive and affective task performance both before and after estrogen or placebo treatment (PT). There will be four successful\* TRP depletion test sequences: two test sequences one week apart prior to ET or PT, and two sequences one week apart following approximately 6-weeks of double-blind ET or PT. Each TRP depletion test day will involve ingestion of 70 capsules. During one of each pair of tests, the 70 capsules will contain 31.5 g of lactose (sham depletion; for participants who are not lactose intolerant) or 31.5 g of microcellulose (sham depletion; for participants who have mild to moderate lactose intolerance), while during the other test they will contain a total of 31.5 g of amino acids, but no tryptophan (see below; Neumeister et al., 2004; Neumeister et al., 2005). The order of the tests (sham vs. active depletion) will be randomly assigned in double blind fashion by the research pharmacist. Imaging procedures will take place on each of the test days. Subjects will be required to remain at the Center for Human Phenomic Science (CHPS) for the entire Test Day except during the fMRI scan.\*\*

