# TRP Depletion Tests:

Each of the four test days will begin in the morning, no later than 7:30 AM, following an overnight fast that begins at midnight and subjects will remain fasting until the end of the test session, approximately 8hours. Subjects will be admitted to a specially designated testing room on the CHPS/PCWBW and will remain in the test room for most of the session, but will be free to walk about the room and the CHPS/PCWBW, use the facilities, and drink water. They will be continuously monitored throughout the day by a trained research nurse, with a medical research investigator available at all times.

Baseline behavioral ratings, blood samples, and vital signs will be taken from 7:30 - 8:00 AM. Initial assessments include measurement of sleep quality (PSQI; test days 2 and 4 only), and hot flash severity (daily diary completed for previous 7 days). Mood will be evaluated using the HAM-D, BDI, POMS, STAI, PSS and VAS. Blood sampling in the morning on each test day will measure estradiol, progesterone, serum hormone binding globulin, DHEA, and baseline tryptophan (total and free) levels. Additionally, on the first test day only, one additional tube of blood will be drawn to examine genetics of estrogen synthesis and metabolism and genes for neurochemicals/systems modulated by estrogen and Version: November 28, 2016 IRB APPLICATION page 18 of 35

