# Randomization to Estrogen Treatment (ET) or Placebo Treatment (PT)

After completing the first two TRP depletion test sequences, participants will be randomized to receive either treatment with 17β-estradiol (Vivelle Dot® 0.10 mg/day) or a look-alike placebo patch for a total of 8 weeks. The research pharmacist who is responsible for dispensing the estrogen or placebo patches will also be responsible for the randomization of all subjects together with the statistician on the study. Randomization will be blocked and stratified. We will use a block size of 3 to be able to maintain a 2:1 ratio of estrogen to placebo within each stratum. To stratify randomization based upon time since last menstrual period by tertiles (1st=0-40 mos; 2nd=40-80 mos; 3rd=80-120 mos), we will prepare separate randomization tables for each stratum. The research pharmacist, PI, and research project manager will know to which group the subject has been randomized. The research pharmacist, PI or research project manager can be reached at any time should it become necessary to unblind a study participant immediately. The subject and all other study-related personnel (clinicians, raters, fMRI technicians, etc.) will be blind to subject assignment.

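### The hot-flash diary comparison is stated only as before versus after, with no estrogen-versus-placebo contrast, although both randomised arms keep the diary

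*Combined protocol and SAP*

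**What the plan says.** The diary is described under METHODS, 1. Study Instruments. Each day's score multiplies the number of hot flashes by their severity and sums the results. On timing: "Subjects will be instructed to complete this form daily throughout the course of their study participation". On who receives it: "This rating is only given to participants who presently report experiencing hot flashes". No minimum frequency or severity is set. On analysis: "The mean for the week prior to testing and the 6th week of ET or PT will be compared".

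Section 4, Statistical Analysis, names methods for imaging, cognition, mood and plasma tryptophan. It also plans correlations of behavioral ratings with tryptophan. It does not mention the diary.

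The design around it is a randomised, blinded comparison. On allocation: "We will use a block size of 3 to be able to maintain a 2:1 ratio of estrogen to placebo within each stratum". The Objectives give "our new sample size of 28 women receiving ET and 14 women receiving placebo". On blinding: "The subject and all other study-related personnel (clinicians, raters, fMRI technicians, etc.) will be blind to subject assignment". The second pair of test days consists of "two sequences one week apart following approximately 6-weeks of double-blind ET or PT". Nothing restricts the diary to one arm.

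**The concern.** The two things set against each other in the diary sentence are two periods. The words ET or PT say which treatment the sixth week belongs to; they do not set one arm against the other. An analyst who followed the sentence literally would test a change over time. That change contains everything the arms share: placebo response, the effect of keeping a diary, the passage of time, and possibly some regression to the mean, because women receive the diary only if they currently have the symptom it measures. Randomisation is what removes these shared components, and the stated comparison does not use it.

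The stake is interpretive. The Background section on early and late use of ET notes that cognitive benefit from hormone therapy may partly reflect relief of menopausal symptoms. Its example is insomnia rather than hot flashes, and it goes on to cite evidence for a cognitive benefit of early estrogen use. If the trial wants to say anything about hot-flash relief beside its cognitive and imaging results, it needs the relief attributable to ET, and a within-arm change does not give that.

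**Working it through.** **Plan's own figure.** None exists. The documents give no SD, effect size, alpha or power for hot flashes, and not the number of women expected to have them. The arm sizes do match the allocation ratio: 28/14 = 2.

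**Inputs.**
- From the Objectives: 28 ET and 14 PT women.
- Assumed: all of them have hot flashes (28+14), or half do (14+7).
- Assumed: two-sided alpha 0.05.
- Assumed: no true estrogen effect, and a fall δ shared by both arms of 0.2 to 0.5 SD of the within-woman change.

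**Before-after test in the ET arm.** The t statistic is noncentral with n − 1 degrees of freedom and noncentrality λ = δ√n.

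| n | critical t | δ | λ | rejection rate |
|---|---|---|---|---|
| 28 | 2.052 | 0.2 | 0.2 × √28 = 1.06 | 17.5% |
| 28 | 2.052 | 0.5 | 0.5 × √28 = 2.65 | 72.3% |
| 14 | 2.160 | 0.2 | 0.2 × √14 = 0.75 | 10.7% |
| 14 | 2.160 | 0.5 | 0.5 × √14 = 1.87 | 41.0% |

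**Between-arm test of change.** λ = (δ − δ)/√(1/n₁ + 1/n₂) = 0, so the rejection rate is 5.0% whatever δ is.

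**Regression to the mean alone.** A simulation of 4,000 trials per setting (28+14 women, no treatment effect, no other change) selected women directly on the baseline weekly mean.
- Lowest quarter excluded: the ET-only test rejected in 7.6%, 14.8% and 20.1% of trials at assumed retest correlations of 0.9, 0.7 and 0.5.
- The between-arm test stayed at 4.3% to 5.4% in every setting run.
- The plan does not select on the diary mean and sets no threshold, so these figures show direction, not size.

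**Price of the between-arm contrast, in SD of change.**
- Standard error with 28+14: √(1/28 + 1/14) = 0.327, against 1/√28 = 0.189 for the ET arm alone, a factor of √3 = 1.73.
- Detectable difference at 80% power with 28+14: (2.021 + 0.851) × 0.327 = 0.94.
- With 14+7: (2.093 + 0.861) × 0.463 = 1.37.
- Baseline adjustment recovers part of this. With equal variances at both times and retest correlation ρ, the ANCOVA residual variance relative to that of change is (1 − ρ²)/(2(1 − ρ)) = (1 + ρ)/2. That is 0.75 at ρ = 0.5 and 0.85 at ρ = 0.7, both assumed.

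**Baseline week.** There are two test days before treatment, one week apart, and the test-day procedures collect the previous 7 days of diary. The week before testing could therefore end at test day 1 or at test day 2. The second choice takes in test day 1 itself, which may be an active depletion day.

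**The case against.** The sentence sits in an instrument description. It names no test and no direction of inference, and it mentions both treatments, so comparing the two arms' changes remains open to the analyst. That is fair. The defect is a contrast left unstated, not a design without a control.

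A reader might go further and infer that a placebo-type fall will be counted as an estrogen effect. The documents do not support that: no section attributes a fall to estrogen, and PT women keep the diary too. For the same reason the rates above are rejection rates and become false claims only if someone reads them as evidence for estrogen. If scores really fall, rejecting no change is correct.

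A reader might also infer that regression to the mean is large. Selection is on currently reporting hot flashes, with no severity threshold, and the baseline is a diary mean rather than the report used for selection. The effect may be small, and nothing in the documents sizes it.

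The diary might arguably fall under the planned correlations of behavioral ratings with plasma tryptophan, since hot-flash severity is among the initial test-day assessments. Even so, that would supply no ET-versus-PT contrast.

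Finally, no aim, hypothesis or power statement concerns hot flashes, and no section plans to use the diary as a covariate or mediator. This stands and limits the importance of the point.

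**Conclusion.** The point holds as a limited one. The stated hot-flash comparison is before versus after, no between-arm contrast is specified anywhere, and a within-arm change cannot isolate estrogen relief. The illustrative size is a rejection rate of about 18% to 72% with 28 ET women, or 11% to 41% with 14, when estrogen does nothing, against about 5% between arms. Those ranges rest wholly on an assumed shared fall of 0.2 to 0.5 SD of change and on assumed numbers of women with hot flashes; the upper pair supposes that every ET woman has them. Reading the baseline as a pre-treatment week is natural but is itself an inference, because the phrase is ambiguous. No main conclusion of the trial depends on this comparison. It is still more than missing detail, because a better standard analysis is available from data both arms already provide.

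**What to change.** Replace the comparison sentence in the diary item with: *Among women given the diary at baseline, the mean daily score in week 6 will be compared between the ET and PT arms, adjusted for the mean daily score in the baseline week (ANCOVA); within-arm changes are descriptive only.* Define the baseline week, for example as the 7 days before test day 1. A between-arm comparison of change or a mixed model would also serve, provided the arm contrast is named in advance.

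The cost is a change of wording, with no new data, visits or participants. The real downside is precision: with the detectable differences shown above, the contrast can pick up only large effects, so it should be reported as an estimate with a confidence interval, and a non-significant result should not be read as absence of relief.
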